2.3 SECONDARY OBJECTIVE

1. To evaluate the safety and tolerability of 4 weeks of LZD 1200 mg for the treatment of TBM.

2. To determine if LZD exposures in the CSF and plasma predict linezolid AEs.

3. To compare longitudinal neurocognitive and functional outcomes in participants randomized to linezolid versus no LZD for the treatment of TBM.

4. To determine if LZD exposures in CSF and plasma predict neurocognitive and functional outcomes.

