2.4 SECONDARY ENDPOINTS

1. Proportion of participants with Grade 3 or higher AEs at 4 weeks

2. Proportion of participants who complete LZD treatment

3. Exposure-response (PK-PD) relationship, with LZD as predictor and Grade 3 or higher AE as outcome variable

4. Modified Rankin Scale (death, severe disability, moderately severe, moderate disability, slight disability, no significant disability, no symptoms) at 12 and 24 weeks

5. Montreal Cognitive Assessment (MoCA) or neurocognitive battery performance at 12 and 24 weeks

6. Exposure-response (PK-PD) relationship, with linezolid as predictor and Modified Rankin Scale as outcome variable

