6.3.13 Laboratory assessments

At screening and entry all laboratory values must be recorded on the CRF. For post-entry assessments, record on the CRF all laboratory values regardless of grade. Blood samples will be collected via venous blood draw.

Hematology

A complete blood count, including hemoglobin, white blood cell count (WBC), differential WBC (to include only neutrophils, lymphocytes, and monocytes), absolute neutrophil count (ANC), and platelet count will be performed.

Liver Function Tests

AST and/or ALT; total and direct bilirubin; and alkaline phosphatase will be performed.

Blood Chemistry

Sodium, potassium, bicarbonate, and creatinine will be performed.

Pregnancy Test

For women of reproductive potential: Serum or urine β -HCG may be used (urine test must have a sensitivity of <25 mIU/mL).

Documentation of HIV infection

HIV-1 infection, documented by any licensed rapid HIV test or HIV-1 E/CIA test kit at any time prior to entry and confirmed by a licensed Western blot or a second antibody test by a method other than the initial rapid HIV and/or E/CIA, or by HIV-1 antigen or plasma HIV-1 RNA viral load. Two or more HIV-1 RNA viral loads of >1,000 copies/mL are also acceptable as documentation of HIV-1 infection, or documentation of HIV diagnosis in the medical record by a healthcare provider.

CD4+ for participants living with HIV

Obtain absolute CD4+ count and percentages at entry unless the results are available within 14 days prior to entry.

Other laboratory testing

Additional laboratory tests can be undertaken at the discretion of the physician with agreement of the site PI.

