10.0 STATISTICAL CONSIDERATIONS

10.1 Sample size estimation

Sample size calculations for the PK analyses are based on different study designs (varying number of participants and time points) using clinical trial simulations. We used the stochastic simulationestimate "sse" methodology for clinical trial simulation and re-estimation to determine sample sizes required to evaluate key PK parameters with precision adequate to determine optimal dosing for a future efficacy trial of LZD. This methodology simulates the data from a planned trial with a proposed design (e.g., number of participants) followed by the estimation of the parameters under the true and alternative models. This is repeated a minimum of 1000 times to estimate PK parameters, standard errors and inter-individual variability. With 30 participants receiving LZD, we will be able to estimate PK parameters with required precision of relative standard errors <10% for typical values and <25% for random effects (inter-individual variability). For the evaluation of LZD adverse events, if we assume 40% of participants in the LZD arm and 10% in the no LZD arm will experience myelosuppression.^{78,84} the planned sample size of 60 participants (n=30 per arm) will provide at least 80% power to detect a similar or greater difference in the frequency of myelosuppression between arms at a significance level of 0.05. Given the modest sample size, we recognize that we may not have adequate power to compare the frequency of myelosuppression in participants on LZD and standard versus high dose RIF; however, if the frequency of myelosuppression in participants on LZD and high dose RIF (n=20) is anticipated as \sim 25%, the 90% confidence interval of this estimate is 10% to 46% with a precision of 18%.

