10.2 Planned analyses

The primary outcomes will be CSF and plasma LZD PK parameters, including CSF to plasma ratio, rate of CSF uptake, and plasma absorption rate constant (k_a), drug clearance (Cl/F), volume of distribution (V_d). We will employ a model-based approach using non-linear mixed effects modeling in NONMEM to estimate plasma and CSF PK parameters based on simultaneous analysis of all plasma and CSF drug concentration data.⁷⁴ We will perform post-hoc Bayesian predictions of secondary LZD PK parameters, including C_{max} , time to C_{max} , AUC₀₋₂₄, and elimination half-life in plasma and in CSF. Based on this approach, we will characterize the dynamic uptake of LZD in the CSF when administered with high and standard dose RIF over 4 weeks and derive a dosing algorithm for LZD to achieve target exposures through simulations. Pharmacodynamic breakpoints for LZD against TB are not established, but we will use target AUC₀₋₂₄, AUC/MIC, T>MIC for LZD of 160 µg*hr/mL, 100, and 85%, respectively.^{23,75,76} We will use sparse sampling to estimate the AUC curve based on CSF sampling early, at steady state, and before LZD discontinuation.⁷⁷

For the LZD adverse event evaluation, the primary outcome will be a dichotomous measure of Grade 3 or higher (yes/no) myelosuppression (e.g., anemia, thrombocytopenia, leukopenia) during the 4 weeks of therapy. A secondary outcome will be LZD discontinuation or dose reduction (yes/no) for any AE. We will compare the frequency of myelosuppression between the LZD and no LZD arms across RIF dosing with the Cochran-Mantel-Haenszel test, which accounts for stratified randomization. Within

the LZD arm, we will explore differences in the frequency of myelosuppression between the standard and two high dose RIF arms combined by a chi-square test. We will use an exposure-response model using logistic regression to test if the probability of myelosuppression and LZD discontinuation is related to PK measurements, including C_{min} , C_{max} and AUC₀₋₂₄.

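### Linezolid exposure is related to myelosuppression only through a yes/no outcome in about 30 participants; a prespecified model of the recorded blood counts should be added beside it

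*Combined protocol and SAP*

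**What the plan says.** Secondary objective 2 (Section 2.3) is "To determine if LZD exposures in the CSF and plasma predict linezolid AEs". The matching endpoint, item 3 of Section 2.4, is "Exposure-response (PK-PD) relationship, with LZD as predictor and Grade 3 or higher AE as outcome variable".

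Section 10.2 turns this into an analysis. For adverse events, "the primary outcome will be a dichotomous measure of Grade 3 or higher (yes/no) myelosuppression" over the 4 weeks of therapy, and "A secondary outcome will be LZD discontinuation or dose reduction (yes/no) for any AE". The exposure analysis is then: "We will use an exposure-response model using logistic regression to test if the probability of myelosuppression and LZD discontinuation is related to PK measurements", with Cmin, Cmax and AUC0-24 listed as the measurements. No lead measurement is named.

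Section 6.3.13 covers hemoglobin, white cells with differential, ANC and platelets, and instructs: "For post-entry assessments, record on the CRF all laboratory values regardless of grade". Table 5 schedules hematology at screening, entry and Weeks 1, 2 and 4. Section 10.2 describes no analysis of these counts as continuous outcomes.

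Section 10.1 fixes the scale: "With 30 participants receiving LZD" for the PK work and, for toxicity, "if we assume 40% of participants in the LZD arm and 10% in the no LZD arm will experience myelosuppression". It gives no power for the exposure-response test.

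**The concern.** Exposure and the blood counts are both continuous. Cutting the counts at Grade 3 before relating them to exposure discards how far each count fell, and it ignores where each participant started. That second loss matters here because the eligibility limits for hemoglobin, platelets and ANC (Section 3.2, item 10) are the same values that trigger the hematological management plan (Section 8.1.2). A participant who enters just above a limit can cross it after a small fall, while one who enters well above it can have a large fall and not be counted.

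At stake is the sensitivity of the answer to secondary objective 2. With about a dozen events, a real relation between concentration and marrow effect has a fair chance of going undetected, when data able to show it more clearly are already on the CRF.

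**Working it through.** **Inputs from the documents.** n = 30 with linezolid exposure; event rate 40%, so 0.40 × 30 = 12 events; significance level 0.05 (Section 10.1, sidedness not stated, taken as two-sided). Expected deaths are about 40% of participants over the study (Section 7.4), used for sensitivity: 0.60 × 30 = 18.

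**Assumed input.** The correlation r between exposure and the severity of the count is not given. The range 0.3 to 0.6 is used.

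**Step 1: the plan's own figure.** Section 10.1 claims at least 80% power for 40% vs 10% with 30 per arm. Unpooled normal approximation: SE = √(0.40×0.60/30 + 0.10×0.90/30) = √0.011 = 0.1049; 0.30/0.1049 = 2.86; power = Φ(2.86 − 1.96) = 81.6%. The pooled version gives 78.0%, arcsine 80.3% and exact Pearson 79.6%. The claim is broadly reproduced, but it concerns linezolid vs no linezolid, not the exposure test.

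**Step 2: one count, yes/no vs continuous.** Exposure and count severity are bivariate normal with correlation r. The event is severity above the cut that gives 40%. The logistic model uses the likelihood-ratio test and the linear model the t test; 100,000 simulated trials per row.

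| r | Linear on count | Logistic | Loss (points) |
|---|---|---|---|
| 0.3 | 36.9% | 27.2% | 9.7 |
| 0.4 | 60.7% | 44.2% | 16.5 |
| 0.5 | 82.9% | 64.2% | 18.6 (unrounded) |
| 0.6 | 95.5% | 82.1% | 13.4 |

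Hand check of the linear column, power ≈ Φ(atanh(r)·√(n−3) − 1.96): at r = 0.5, Φ(0.549 × 5.196 − 1.96) = Φ(0.89) = 81%. At r = 0 the rejection rates were 5.0% (linear) and 5.9% (logistic), so the gain does not come from inflated error.

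**Step 3: sensitivity.** With a Wald test for the logistic model the losses are about 17 to 29 points. At r = 0.7 the likelihood-ratio loss is about 5 points. With n = 24 the losses over r = 0.3 to 0.6 are 7 to 18 points, and with n = 18 they are 3 to 17. Adding the entry count to the linear model, assumed to correlate 0.5 with the residual (also not in the documents), raises linear power to about 45%, 71%, 90% and 99% at the four values of r.

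**Step 4: three counts.** The plan's event covers anemia, thrombocytopenia and leukopenia. The event is now any of three counts beyond a common cut, with 40% events overall; 20,000 trials. Ranges cover independent residuals and residuals correlated 0.3.

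| Counts related to exposure | Logistic on composite | One pre-chosen count | Three counts, Bonferroni |
|---|---|---|---|
| All three, r = 0.3 | 35–41% | 37% | 45–51% |
| All three, r = 0.5 | 77–83% | 83% | 92–96% |
| One only, r = 0.5 | 16–18% | 83% if it is the right count | 70% |

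If Bonferroni must also cover two exposure metrics (assumed correlated 0.8), power with all three counts at r = 0.3 and independent residuals falls to about 43%, against 41–43% for logistic: essentially no gain. With no correction, three independent tests have a family-wise error of 1 − 0.95³ = 14.3%.

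**The case against.** The logistic model matches the declared endpoint. Item 3 of Section 2.4 names Grade 3 or higher AEs as the outcome, and that category is clinically readable. Blood counts cannot stand in for hepatic, gastrointestinal or neurological events, or for discontinuation for any AE. This stands: the count model should be added, and the logistic models should not be demoted.

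The simulation also flatters the linear model, with one normal count, a straight-line relation and complete data. In the trial, linezolid is stopped at count thresholds and may be resumed at a reduced dose (Section 8.1.2), so later exposure partly depends on the count. Participants who die early have fewer counts, so their lowest value is not comparable. This also stands, and it shapes the fix.

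A reader might infer more than the documents support in three ways:

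- *That a missed slope would misdirect the dosing algorithm.* Section 10.2 derives that algorithm by simulation to reach PK target exposures, and Section 10.1 ties dosing to the precision of PK parameters. Neither says that a toxicity slope enters.
- *That the event rate is 25% or 5%, leaving few or no events to model.* The 25% in Section 10.1 is for linezolid with high-dose rifampicin only. The 5% in the background section comes from patients with gram-positive infections on another schedule. The plan's figure for the linezolid arm is 40%.
- *That the planned test will probably miss a real effect.* At 40% events its power is 64% at r = 0.5 and 82% at r = 0.6. At r = 0.3 the unadjusted linear model also misses more often than not (36.9% power).

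**Conclusion.** The point holds as a low-cost improvement to a secondary analysis. For myelosuppression, reducing the recorded counts to yes/no costs about 10 to 19 points of power in a one-count illustration (n = 30, 40% events, likelihood-ratio test, assumed r of 0.3 to 0.6). It would be wrong to read that range as the gain from any particular three-count analysis. That gain runs from essentially none (all counts weakly related, correction across two metrics as well) to more than 50 points (one count related, Bonferroni across three: 70% vs at most 18%). Nor does it extend to linezolid discontinuation or to non-hematological Grade 3+ events. With one named metric and Bonferroni across three counts, the count models had more power than the logistic model in every scenario in the three-count table, so the addition is worthwhile if those choices are fixed in advance.

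**What to change.** In Section 10.2:

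1. Keep the logistic models for the declared Grade 3+ and discontinuation endpoints, with a penalised (Firth) fit if events are few.
2. Add a linear model of the lowest scheduled hemoglobin, platelet count and ANC through Week 4 (log scale for platelets and ANC), adjusted for the entry value of the same count.
3. Name one exposure metric for this model in advance. Also name either a lead count or a Bonferroni or Holm correction across the three.
4. Define exposure at the assigned dose, for example from PK data collected before any linezolid interruption, so that stopping or reducing the drug because of a low count does not feed back into the predictor.
5. State how participants who die early and have fewer counts are handled.

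The cost is a paragraph of text and some programming, with no new visits, samples or participants. The slopes will be in count units and must be translated into Grade 3+ risk from the fitted model, and correcting across three counts costs a little power.

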11.0 DATA COLLECTION AND MONITORING

11.1 Records to be Kept

Case report forms (eCRFs) will be provided for each participant. Participants must not be identified by name on any CRFs. Participants will be identified by a participant identification number (PID).

11.2 Clinical Site Monitoring and Record Availability

The PI and site PI will visit the site to review individual participant records, including consent forms, CRFs, supporting data, laboratory specimen records, and medical records (physicians' progress notes, nurses' notes, participants' hospital charts), to ensure protection of study participants, compliance with the protocol, and accuracy and completeness of records. The monitors also will inspect sites' regulatory files to ensure that regulatory requirements are being followed and sites' pharmacies to review product storage and management.

The site investigator will also make study documents (e.g., consent forms, drug distribution forms, CRFs) and pertinent hospital or clinic records readily available for inspection by the local IRB, study sponsors, or other designated local, US, and international regulatory authorities for confirmation of the study data.

Study data forms will be digitally scanned for permanent record keeping and to enable rapid resolution of any discrepancies. The DSMB and regulatory inspectors will have full access to source documents. The following data will be verifiable from source documents:

- Signed consent forms
- o Dates of assessments including dates specimens were processed in the laboratory
- Eligibility and baseline values for all participants
- o Clinical endpoints
- Adverse events
- o Participant clinical and laboratory data
- Study drug compliance
- Pharmacy logs for dispensing / returns of study drugs
- Concomitant medication

11.3 Role of Data Management

The study paper-based CRF is the primary data collection instrument for the study. All data requested on the CRF will be recorded. Entering study data on CRFs will be performed in a timely fashion by the site.

11.4 Data collection, Entry and Retention

Data collection is the responsibility of the study staff under the supervision of the PI and site PI. The investigator is responsible for ensuring accuracy, completeness, legibility and timeliness of data

collection and entry. The investigator will retain study essential source documents for 20-years after the completion of the study, as per Ugandan guidelines. Digital images of the source documents will be retained for an indefinite period.

11.5 **Protocol violations**

A protocol deviation is any noncompliance with the clinical trial protocol or GCP requirements with an impact on patient safety or scientific integrity. The noncompliance may be either on the part of the participant, the investigator or study site staff. Corrective actions are to be developed by the PI and implemented promptly. It is the responsibility of the site to be vigilant, to identify and report deviations within 5 working days on the deviation. All deviations must be addressed in source documents and sent to local IRB as per their guidelines.

As this trial duration is 24 weeks, reportable deviations include:

- 1) Participant Eligibility Criteria
- 2) Informed Consent
- 3) Randomization Procedures
- 4) Administration of Study Investigational medicine

11.6 Laboratory Quality Control

All laboratory work will be undertaken in accredited laboratories with internal and external validation procedures.

12.0 ETHICS AND PROTECTION OF HUMAN SUBJECTS

This study is to be conducted according to the international standards of Good Clinical Practice (International Conference on Harmonization guidelines), Declaration of Helsinki, and International Ethical Guidelines for Biomedical Research Involving Human Subjects, applicable national government regulations, and Institutional research policies and procedures. All investigators must have received human subject protection and GCP training prior to human subject involvement.

12.1 Institutional Review Board (IRB) Review and Informed Consent

This protocol, the informed consent documents, and any subsequent modifications will be reviewed and approved by the appropriate IRB/ethics committees. A signed consent form will be obtained from the participant (or proxy for participants who cannot consent for themselves). The consent form will describe the purpose of the study, the procedures to be followed, and the risks and benefits of participation. A copy of the consent form will be given to the participant or proxy and if they are unwilling to keep a copy, it will be kept at the study site on their behalf.

12.2 Participant Confidentiality

All participant-related information, including laboratory specimens, CRFs, and other records will be kept confidential and identified by participant ID only to maintain confidentiality. All records will be kept in a secure, locked location and only research staff will have access to the records. All computerized databases will identify participants by numeric codes only, and will be password-protected. Clinical information will not be released without written permission of the participant, except as necessary for monitoring by local, US, or international regulatory authorities as part of their duties, or the study sponsor.

12.3 Study Discontinuation

The study may be discontinued at any time by the IRB, study sponsor, independent DSMB, or other regulatory agencies as part of their duties to ensure that research participants are protected.

12.4 Future Use of Stored Specimens

If *additional* storage consent has been given residual participant specimens will be stored for future research. Specimens to be stored include CSF and blood.

12.5 Conflict of Interest

No conflict of interest exists by any investigator. Any investigator who develops a new conflict of interest will disclose this to their relevant institutional oversight board and to the study sponsor.

13.0 PUBLICATION OF RESEARCH FINDINGS

All publications and presentations relating to the study will be authorized by the trial investigators. Named authors will include at least the trial's PI, site PI, co-investigators, and statistician. Members of the DSMB will be listed as contributors if published in a journal where this does not conflict with the journal's policy.

